### **5.5 Safety Analyses**

#### **5.5.1 Extent of Exposure**

GEN3014 will be administered as weight adjusted IV infusion (mg/kg) in 4-week (ie, 28-day) cycles as follows: every week (Q1W) in Cycles 1 and 2, every 2 weeks (Q2W) in Cycles 3 through 6, and every 4 weeks (Q4W) from Cycle 7. Please note that the first dose will be equally split on C1D1 and C1D2. In Expansion Part B daratumumab SC will be administered as an SC flat dose (mg) injection at the same scheduled frequency.

Number of cycles initiated, duration of exposure, number of trial drug administrations (number of full dose infusions of GEN3014 and number of SC injections of daratumumab) and dose level (mg) per trial drug administration (on full dose infusions for GEN3014) will be summarized with descriptive statistics (n, mean, standard deviation (Std Dev), median, minimum, and maximum). The number and percentage of subjects with dose interruptions, delay, reasons for dose

interruptions (adverse event, drug administration issues, or other), and reasons for dose delay (adverse event, drug administration issues, or other) will be presented.

GEN3014 specific exposure statistics such as duration of full dose infusion (hours) and dose level per full dose infusion (mg/kg) will be provided. In these two statistics the split doses will not be included as they would bias the result.

#### 5.5.1.1 *Duration of Exposure*

Duration of exposure in *months* is defined as

- $(\text{end of treatment date} - \text{date of first drug administration} + 1) / 30.4375$

Duration of exposure in *cycles* is defined as

- $(\text{end of treatment date} - \text{date of first drug administration} + 1) / 28$

where *end of treatment date* is defined as

- $\min(\text{last date of trial drug administration} + \text{number of days up to next expected trial drug administration} - 1; \text{last contact date}; \text{date of administrative cut-off}; \text{date of death})$

For cycle-specific statistics, date of first drug administration and date of last treatment administration will be derived for each period e.g. Cycle 1-2 (Q1W), Cycle 3-6 (Q2W) and Cycle 7+ (Q4W). Start date of each cycle specific-period is date of first trial drug administration in that period, and end date of each cycle-specific period will be *min*(date of starting next cycle-specific period (if any); end of treatment date).

#### 5.5.1.2 *Relative Dose Intensity*

Dose intensity statistics will be summarized for the cycle-specific periods. Only subjects entering Cycle 3 per eCRF will be considered to contribute to Cycle 3-6 statistics below. Similar for Cycle 7+.

The planned dose intensity for Cycle 1-2 is dose level x 4 (mg/kg/cycle), for Cycle 3-6 it is dose level x 2 (mg/kg/cycle) and for Cycle 7+ it is dose level x 1 (mg/kg/cycle), where the subject's weight in kilogram (kg) should be the last obtained weight used for dose calibration at trial drug administration visit. Note that for the initial level 0.2/0.6 (mg/kg), the planned dose intensity for Cycle 1-2 is  $(0.2+0.6 \times 3+0.6 \times 4) / 2$  (mg/kg/cycle).

Actual cumulative dose received (mg/kg), is calculated as the sum of all doses administered in the cycle-specific period, and will be summarized using descriptive statistics.

The relative dose intensity (%) is defined as

$$\frac{\text{Actual cycle-specific cumulative dose (mg/kg)} / \text{Duration of cycle-specific exposure (cycles)}}{\text{Cycle-specific planned dose intensity}}$$

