#### **6.6.2 GEN3014 Dose Modification Guidance and Stopping Criteria (Dose Escalation and Expansion Part A)**

- No dose modification (increase or decrease) of GEN3014 will be permitted for this trial.
- If a subject experiences a DLT, the subject may continue treatment with GEN3014, if the toxicity recovers to  $\leq$  grade 2 or baseline within 4 weeks from occurrence of the DLT. Continued administration of GEN3014 must be agreed to between the sponsor and the investigator based on a thorough assessment of the event, the duration of the event, and benefit-risk for the subject. In the event a subject experiences a second episode of a DLT with GEN3014, the treatment will be permanently discontinued. Treatment with GEN3014 will be discontinued in the event the DLT is not resolved within 4 weeks.
- If a subject experiences toxicity that would have qualified as a DLT but the event occurs after the DLT evaluation period, the subject's benefit-risk must be thoroughly assessed. Continued treatment with GEN3014 must be agreed between the sponsor and the investigator.
- For the subject who receives treatment beyond the DLT evaluation period, all corresponding AEs that would have met the DLT criteria will be considered for the purpose of determining the RP2D and/or MTD (if reached). For the declaration of the RP2D from the Dose Escalation for further development of GEN3014 in the Expansion, the totality of the data including safety, PK, pharmacodynamics, and preliminary efficacy will be evaluated.
- During the trial, a planned dose of GEN3014 can be postponed for up to 4 weeks due to an AE whether it is considered drug-related or not.

- In case of dose delay of more than 4 weeks from the last trial drug administration due to toxicity, GEN3014 should be discontinued, unless resuming administration of GEN3014 is agreed between the sponsor and the investigator.
- During the trial, the GEN3014 dose can be held for the following laboratory results:
  - a. If platelet count is  $<50 \times 10^9/L$ , hold dose until platelet count is  $\geq 50 \times 10^9/L$ .
  - b. If febrile neutropenia is  $<0.5 \times 10^9/L$ , hold dose until neutrophil count is  $\geq 0.5 \times 10^9/L$ .
  - c. If hemoglobin is  $<8$  g/dL ( $<8$  g/L or  $<5$  mmol/L), hold dose until hemoglobin is  $\geq 8$  g/mL ( $\geq 8$  g/L or  $\geq 5$  mmol/L).

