## 1.1 Objectives and Endpoints

**Table 1: Phase 1 Dose Escalation**

Objectives	Endpoints
Primary	

 
Determine the RP2D and if reached, the MTD of GEN3014
 
	
 
Incidence of DLTs
 

 
Evaluate the safety and tolerability of GEN3014
 
	
 
Safety: Incidence and severity of AEs and SAEs, including changes in laboratory values, vital signs, ECGs
 
Tolerability: Dose interruptions, delay, and dose intensity
 

Secondary	

 
Characterize the PK properties of GEN3014
 
	
 
Noncompartmental PK parameters (if feasible): 
 
Cmax
 
tmax
 
Ctrough
 
AUC0-last and AUC0-168h
 
RA,Cmax and RA,AUC
 
 
 
In addition, a population PK modeling approach may be employed
 

 
Characterize the pharmacodynamic properties of GEN3014
 
	
 
Pharmacodynamic markers in blood and tumor samples, including frequencies of NK cells and other leukocyte subsets and complement analyses
 

 
Evaluate immunogenicity
 
	
 
Anti-GEN3014 antibodies
 

 
Assess the preliminary anti-tumor activity of GEN3014
 
	
 
ORR
 
CBR
 
DOR
 
TTR
 

 
Assess the clinical efficacy of GEN3014
 
	
 
Progression-free survival (PFS)
 
Overall survival (OS)
 

Exploratory	

 
Assess potential biomarkers predictive of clinical response to GEN3014
 
	
 
Expression of CD38 and other molecular markers on tumor cells at baseline and during treatment
 

 
Assess minimal residual disease (MRD) status
 
	
 
Rate of MRD-negative remission in RRMM
 

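### Relative dose intensity is inflated, and about one missed dose can be masked, when a subject's final dosing period is cut short at cut-off, death or last contact

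*SAP*

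**What the plan says.** SAP 5.5.1.2 reports RDI separately for Cycles 1-2, Cycles 3-6 and Cycle 7 onward. It is the actual cumulative dose in the period, divided by the period's duration in 28-day cycles, divided by the planned dose intensity. The planned intensity is 4, 2 and 1 times the dose level per cycle in the three periods. The numerator is defined as follows: "Actual cumulative dose received (mg/kg), is calculated as the sum of all doses administered in the cycle-specific period". SAP 5.5.1.3 applies the same approach in mg to both arms of Part B.

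SAP 5.5.1.1 supplies the duration. End of treatment is the earliest of four dates. The first is the last administration plus the "number of days up to next expected trial drug administration" minus 1. The others are last contact, the "date of administrative cut-off" and death. A period ends at the earlier of "date of starting next cycle-specific period (if any); end of treatment date".

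SAP Table 1 lists among the primary Dose Escalation endpoints "Tolerability: Dose interruptions, delay, and dose intensity". SAP 1.2 places the primary analyses at the latest 6 months after the last subject's first dose.

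**The concern.** The numerator and denominator treat the last dose differently. The dose is counted whole, while the time it covers is cut whenever cut-off, death or last contact comes before the next dose is due. The ratio can then only move upward.

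This matters for two kinds of subject: those still on treatment at a data cut, and those who die soon after a dose. A subject who received exactly what was planned appears over-dosed, although Protocol 6.6.2 states "No dose modification (increase or decrease) of GEN3014 will be permitted for this trial" (Protocol 6.6.3.1 says the same for Part B). A subject who missed one dose can appear almost fully dosed. Exposure is summarised with means and extremes, so a few one-dose values in the Cycle 7+ period could dominate that summary at an early cut.

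**Working it through.** **Inputs.** Dosing is "every week (Q1W) in Cycles 1 and 2, every 2 weeks (Q2W) in Cycles 3 through 6, and every 4 weeks (Q4W) from Cycle 7" (SAP 5.5.1), so the intervals I are 7, 14 and 28 days. Planned doses per cycle p are 4, 2 and 1 (SAP 5.5.1.2). Duration is end date minus first dose date plus 1 (SAP 5.5.1.1).

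**The plan's own figures reproduce.** 28/7 = 4, 28/14 = 2 and 28/28 = 1. For the 0.2/0.6 mg/kg level, the SAP expression (0.2 + 0.6×3 + 0.6×4)/2 is 2.2 mg/kg/cycle. Protocol Table 4-1 gives the same: (0.1×2 + 0.3×2 + 0.6 + 0.6 + 0.6×4)/2 = 2.2.

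**Formula.** For an on-schedule subject with k doses in the final period and d days counted from the last dose to the cap (d = 1 is the dosing day):

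RDI = k / {[(k − 1)·I + d]/28} / p

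With no cap, d = I and RDI = 100%. With a cap, RDI exceeds 100% for every d below I: 6 of 7, 13 of 14 and 27 of 28 possible days for the three schedules.

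**At the latest primary cut.** C7D1 is day 6×28 + 1 = 169. A cut-off on day 182 leaves 14 days, so RDI = 1/(14/28) = 200%. On day 183 it is 1/(15/28) = 186.7%.

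**Cycle 7+, all doses given on schedule:**

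| Doses | Cap 14 days after last dose (d = 15) | Cap on last dosing day (d = 1, maximum) |
|---|---|---|
| 1 | 186.7% | 2800% |
| 2 | 56/43 = 130.2% | 56/29 = 193.1% |
| 6 | 168/155 = 108.4% | 168/141 = 119.1% |
| 12 | 336/323 = 104.0% | 336/309 = 108.7% |

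Earlier periods: eight doses give at most 8/(50/28)/4 = 112.0% in Cycles 1-2 and 8/(99/28)/2 = 113.1% in Cycles 3-6. Death on day 10 after two weekly doses gives 2/(10/28)/4 = 140%.

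**Masking.** One dose missed mid-period, last planned dose given, cap on that day:

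- Q4W, 5 of 6: 5/(141/28) = 99.3% against 5/6 = 83.3%.
- Q4W, 2 of 3: 2/(57/28) = 98.2% against 66.7%.
- Q1W, 7 of 8: 7/(50/28)/4 = 98.0% against 87.5%.

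Two missed doses stay visible: 4/(141/28) = 79.4% against 66.7% (Q4W, 4 of 6), and 6/(50/28)/4 = 84.0% against 75.0% (Q1W, 6 of 8).

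**Where there is no cap.** A fully dosed final period gives exactly 100%, and a mid-period miss lowers RDI as it should (7 of 8 gives 87.5%). A subject who moves on falls slightly below 100%, because the next period's start day is counted: 8/(57/28)/4 = 98.2% in Cycles 1-2 and 8/(113/28)/2 = 99.1% in Cycles 3-6.

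**Trailing misses.** If Days 1 and 8 are given, Days 15 and 22 are not, and contact continues, exposure ends on day 14 and RDI = 2/(14/28)/4 = 100%. That comes from the uncapped end-date term, so removing the caps alone would not correct it.

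**The case against.** A reader might infer that fully dosed subjects generally exceed 100%. The documents do not support that. A cap acts only on a subject's final period, and only before the next dose is due. Subjects who stop treatment have a safety visit at 30 days and survival contact every 3 months (Protocol 7.1.1, 7.1.2). The longest dosing interval is 28 days, so last contact will usually not bind for them. Protocol 4.4.1 expects about 4 months of treatment and 17 of follow-up in myeloma, so many subjects will never be capped.

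A reader might also infer that missed doses are hidden in general. At most about one is masked, in one capped period. SAP 5.5.1 separately tabulates administrations, interruptions and delays, and SAP 5.5.1.2 summarises cumulative dose, so the information survives elsewhere.

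The largest percentages are one-dose cases. A value slightly above 100% is not in itself an error either, since visit windows of ±3 days can produce it. The consequence is limited: there are no hypotheses, escalation follows DLT counts, the RP2D rests on the totality of data and is already set at 16 mg/kg, and Part B lists no tolerability endpoint. A bias between arms or dose levels would need different proportions of capped subjects, which the documents do not show.

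Finally, Protocol 9.4.2 defines dose intensity as cumulative dose over actual duration of exposure, and the SAP follows it. That stands for dose intensity. It defines neither RDI nor the caps, which are SAP choices.

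These points narrow the concern. They do not explain why a subject dosed exactly to plan should be reported at 200%.

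**Conclusion.** The concern holds in limited form. For a subject whose final period is capped before the next dose is due, the stated formula overstates RDI and can mask about one missed dose. The size depends on the number of doses in that period: 200% after one Cycle 7+ dose with cut-off at day 182, at most 119% after six and 109% after twelve. Uncapped final periods are unaffected.

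The figures assume dosing exactly on schedule, and the maxima assume a cap on the last dosing day. How many subjects are affected cannot be derived from the documents. They would mainly be those ongoing at a data cut or dying soon after a dose. Dose intensity is a named primary tolerability measure in Dose Escalation and the planned cuts can trigger the fault, so the derivation should be corrected. No efficacy or dose-selection conclusion depends on it alone.

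**What to change.** In SAP 5.5.1.2, and by reference 5.5.1.3, define RDI as the actual cumulative dose in the period divided by the planned cumulative dose for the administrations scheduled in that period. Count scheduled administrations up to the date the subject moves to the next period, permanently stops treatment, dies or reaches the cut-off, with each due dose counted in full. State how due dates are set after a delay.

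Checks: one Cycle 7+ dose with cut-off at day 182 gives 1/1 = 100%, and five of six gives 83.3%. A fully dosed subject who moves on gives 8/8 = 100%. Days 1 and 8 given, Days 15 and 22 missed, with a permanent stop recorded after Day 22 and before the next due dose, gives 2/4 = 50%.

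Keep the capped end date for duration of exposure, where it is appropriate. If a duration-based RDI is preferred, let the final period run to last dose + dosing interval − 1 without the caps, and state that this version does not show doses missed after the last one given.

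The cost is about one SAP sentence and one derivation line, with no new data. If the sponsor reads this as a departure from Protocol 9.4.2, it also needs an entry in SAP Appendix 1 (6.1).

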### 5.5.1.3 *Relative Dose Intensity Expansion Part B*

For Expansion Part B the actual cumulative dose and relative dose intensity will be summarized similarly to as described in Section 5.5.1.2, with the exception that the unit of administered trial drug is mg (and not mg/kg).

The planned dose intensity (mg/cycle) for daratumumab SC is for Cycle 1-2 1800 x 4 mg/cycle, for Cycle 3-6 1800 x 2 mg/cycle and for Cycle 7+ 1800 mg/cycle.

The relative dose intensity for GEN3014 and daratumumab SC will be summarized as described in Section 5.5.1.2.

## 5.5.2 *Adverse Events*

### 5.5.2.1 *Definition Treatment Emergent Adverse Event*

A treatment emergent adverse event (TEAE) is defined as any AE with an onset date or worsening grade (relative to the last reported grade before the on-treatment period) within the on-treatment period, defined in Section 5.1.1.2.

A pre-treatment AE is defined as any non-treatment emergent AE with onset during the pre-treatment period, with no worsening during the on-treatment period.

Only SAEs judged by the investigator as related to GEN3014 should be reported during the post-treatment period.

### 5.5.2.2 *Summaries of Treatment Emergent Adverse Events*

Treatment emergent adverse events are summarized by subject incidence rates; therefore, in any tabulation, a subject contributes only once to the count for a given SOC or PT, i.e., the most related occurrence, the event with the worst toxicity grade or the most severe occurrence. For derivation of the worst toxicity grade, all grade changes occurring at or after the time where the event becomes treatment emergent will be considered.

Adverse events will be coded using Medical Dictionary for Regulatory Activities (MedDRA Version 25.0 or higher) and the severity of an AE, or the toxicity grade, will be based on NCI-CTCAE v5.0 (NCI-CTCAE, 2017), except for clinical TLS which is graded according to Cairo-Bishop et al (Coiffier et al, 2008); please note TLS will be included in all summaries below.

The following summaries of TEAEs will be provided:

- Overview of TEAEs

The following summaries will be tabulated by both SOC and PT, and/or by PT depending on relevance:

- TEAEs
- DLTs
- Most common (at least 10%) TEAEs
- Related TEAEs
- TEAEs by worst toxicity grade
- Grade 3 or higher TEAEs
- Most common (at least 5%) grade 3 or higher TEAEs
- Grade 3 or higher related TEAEs
- Fatal TEAEs (i.e., those TEAEs with Grade 5)
- Serious TEAEs
- Serious related TEAEs
- TEAEs leading to dose interruption
- TEAEs leading to dose delays
- TEAEs leading to withdrawal from trial treatment (i.e. drug withdrawn)

The following will also be tabulated

- TEAEs by SOC, PT and worst toxicity grade
- TEAEs by PT and worst toxicity grade
- Serious TEAEs by SOC, PT and worst toxicity grade
- Serious TEAEs by PT and worst toxicity grade

All adverse events will be listed by subject, with flags distinguishing pre-treatment, treatment emergent and post-treatment AEs.

Additional listings will be presented for all SAEs, all AEs leading to treatment discontinuation, and all AEs leading dose interruption or rate changes.

#### 5.5.2.3 *Adverse Events of Special Interest*

IRRs will be considered as AESIs for GEN3014. The corresponding AESI for subcutaneous daratumumab SC are systemic administration-related reactions (sARR).

The number and percentage of subjects with treatment emergent adverse event of special interest will be presented by SOC, PT and worst toxicity grade. Additionally, the number and percentage of subjects with treatment emergent adverse event of special interest leading to treatment discontinuation and dose interruption will be summarized. Time to onset of first IRR, and time to resolution (for resolved cases) will be presented.

### **5.5.3      *Treatment Emergent Fatal AEs and Deaths***

The number and percentage of subjects who died due to related TEAE will be summarized by PT. All fatal adverse events will be presented in a separate listing, indicating relationship to treatment.

All deaths as reported on the eCRF death form will be summarized by primary cause of death. In addition, deaths occurring within 30 or 60 days of first GEN3014 dose, or within 30 or 60 days of last GEN3014 dose will be summarized by primary cause of death.

### **5.5.4      *Additional Safety Assessments (if applicable)***

#### **5.5.4.1      *Clinical Laboratory Data***

Grading of laboratory values will be assigned programmatically as per CTCAE v5.0. The calculation of CTCAE grades will be based on the observed laboratory values only; clinical assessments will not be considered.

CTCAE Grade 0 will be assigned for all non-missing values not graded as 1 or higher.

For laboratory tests where grades are not defined by the CTCAE, results will be categorized as low/normal/high based on laboratory normal ranges.

The following summaries will be generated separately for hematology and biochemistry tests:

- Listing of laboratory data with values flagged to show the corresponding CTCAE term and CTCAE grades, if applicable, and the classifications relative to the laboratory normal ranges.

For laboratory tests where grades that are defined with a CTCAE term:

- Worst post-baseline on-treatment CTCAE grade (regardless of the baseline status). Each subject will be counted only once for the worst grade observed post-baseline.
- Shift tables using CTCAE grades to compare baseline to the worst on-treatment value.
- Summary table of Grade 3 or higher CTCAE graded laboratory toxicities

For laboratory tests where grades are not defined by a CTCAE term:

- Shift tables using the “low/normal/high” classification to compare baseline to the worst on-treatment value

#### **5.5.4.2      *Vital Signs***

The number and percentage of subjects meeting the below criteria at any post-baseline assessment will be summarized by cohort.

#### ***Clinically notable elevated values***

- Systolic BP:  $\geq 180$  mmHg and an increase  $\geq 20$  mmHg from baseline
- Diastolic BP:  $\geq 105$  mmHg and an increase  $\geq 15$  mmHg from baseline
- Weight: Increase of  $\geq 10\%$  from baseline

- Heart rate:  $\geq 120$  bpm with an increase of  $\geq 15$  bpm from baseline
- Temperature:  $> 38^{\circ}$  C

*Clinically notable below normal values*

- Systolic BP:  $\leq 90$  mmHg and a decrease  $\geq 20$  mmHg from baseline
- Diastolic BP:  $\leq 50$  mmHg and a decrease  $\geq 15$  mmHg from baseline
- Weight: decrease of  $\geq 10\%$  from baseline
- Heart rate:  $\leq 50$  bpm and a decrease  $\geq 15$  bpm from baseline
- Temperature:  $< 35^{\circ}$  C

5.5.4.3 ECG

The ECGs will be recorded digitally at the sites by using the standard 12-leads. The digital ECGs will be electronically transmitted from the sites to a central laboratory for a measurement of the cardiac intervals and morphologic assessment by a central cardiologist.

The corrected QT interval (QTc) will be calculated using Fridericia's formula:

$$QT_{cF} = \frac{QT}{\sqrt[3]{\frac{RR}{(1s)}}}$$

The number and percentage of subjects meeting the below criteria at any post-baseline assessment will be summarized by cohort

*Highest post-baseline QTcF interval*

- QTcF interval  $> 450$  msec
- QTcF interval  $> 480$  msec
- QTcF interval  $> 500$  msec

*Change from baseline in QTc interval*

- QTcF interval increases from baseline  $> 30$  msec
- QTcF interval increases from baseline  $> 60$  msec

An overall interpretation of the ECGs will be performed by the investigator, or the investigator may delegate this task to a cardiologist, if applicable. The investigator ECG interpretation must be done using the paper ECG reading from the ECG machine by signing and dating the printout. In case of discrepancy between central and the investigator ECG readings, the central reading will be used for trial analysis purposes.

The concentration of GEN3014, or daratumumab, in the serum samples will be determined by a validated, specific, and sensitive ligand binding assay, at the assay CRO. Based on the concentrations the sponsor will calculate the PK parameters (listed below) based on non-compartmental (NCA) methods.

The PK analysis and output to be generated are detailed in the next paragraphs. In short, GEN3014, or daratumumab, concentration data will be presented graphically and summarized by groups. Graphical exploration of dose-response will be presented.

